Version Date : (Version 8, 11/19/2024)

studies have shown that the prevalence of non-cardiac chest pain is approximately 19-33% , ^{12,13}

Further generation-based analysis of the population with psychogenic chest pain revealed that approximately 32-35% of them were diagnosed with functional chest pain.¹⁴ In terms of reflux hypersensitivity, among patients with non-erosive mucosal damage in the esophagus, approximately 10-36% are diagnosed with esophageal hypersensitivity.^{15,16} Functional heartburn has an unknown prevalence due to the limitations of current diagnostic tools and receiver operating characteristic (ROC) curves. Globus, on the other hand, is a commonly encountered disorder of gut-brain axis interaction in clinical practice. Research reports indicate that 46% of healthy adults have experienced globus at some point.¹⁷ Functional dysphagia is the least common, and its prevalence remains unclear to this day.

In terms of definition, patients must have chronic esophageal symptoms lasting at least three months, with the first occurrence of symptoms being more than six months before the diagnosis of the disease. Additionally, structural, inflammatory, motility, and metabolic abnormalities in the esophagus must be excluded.¹ Therefore, to diagnose esophageal disorders related to gut-brain axis interaction, upper gastrointestinal endoscopy, esophageal pH-impedance testing, and high-resolution esophageal manometry are required to exclude other esophageal diseases that may cause similar symptoms. Regarding the pathophysiological mechanisms, it is currently believed that they may be related to esophageal visceral hypersensitivity and hypervigilance, but the exact mechanisms still require further research for confirmation. In terms of diagnostic criteria, according to the Rome IV criteria, the definition is as follows:¹¹

➤ **Functional Chest Pain:**

- (1) Occurs ≥ 1 time per week with non-cardiac chest pain or chest tightness;
- (2) No associated heartburn or dysphagia;
- (3) Symptoms are not related to gastroesophageal reflux disease (GERD) or eosinophilic esophagitis;
- (4) No significant esophageal motility disorders.

➤ **Functional Heartburn:**

- (1) Occurs ≥ 2 times per week with substernal symptoms such as heartburn or chest pain;
- (2) Symptoms do not improve with antisecretory therapy;
- (3) Symptoms are not related to gastroesophageal reflux disease (GERD) or eosinophilic esophagitis;
- (4) No significant esophageal motility disorders.

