➤ **Reflux Hypersensitivity (Esophageal Hypersensitivity):**

- (1) Occurs ≥ 2 times per week with substernal symptoms such as heartburn or chest pain;
- (2) Endoscopy is normal, and eosinophilic esophagitis must be excluded;
- (3) No significant esophageal motility disorders;

(4) Esophageal pH or pH-impedance testing shows normal acid exposure levels, but reflux is associated with symptoms.

➤ **Globus:**

- (1) Occurs ≥ 1 time per week with persistent or intermittent, non-painful sensation of a lump in the throat, with no organic lesions confirmed through clinical examination, laryngoscopy, or endoscopy;
- (2) Symptoms occur between meals, with no dysphagia or odynophagia, and no gastric metaplasia in the proximal esophagus (gastric inlet patch);
- (3) Symptoms are not related to gastroesophageal reflux disease (GERD) or eosinophilic esophagitis;
- (4) No significant esophageal motility disorders.

➤ **Functional Dysphagia:**

- (1) Occurs ≥ 1 time per week with a sensation of obstruction or abnormal feeling when solids or liquids pass through the esophagus;
- (2) Symptoms are not related to esophageal mucosal or structural abnormalities;
- (3) Symptoms are not related to gastroesophageal reflux disease (GERD) or eosinophilic esophagitis;
- (4) No significant esophageal motility disorders.

[figure not shown]

Figure 1: Diagnostic Spectrum Classification of Gastroesophageal Reflux Disease (GERD) and Disorders of Gut-Brain Axis Interaction (DGBI).

◆ **Physiological Tests for Diagnosing Gastroesophageal Reflux Disease (GERD) and Disorders of Gut-Brain Axis Interaction (DGBI)**

The current diagnosis of gastroesophageal reflux disease (GERD) spectrum disorders is based on endoscopic examination, esophageal pH (or pH-impedance) testing results, and the association between reflux and symptoms. Among these, esophageal pH testing, specifically the acid exposure time (AET), is the most important pathophysiological parameter used to differentiate GERD from disorders of gut-brain axis interaction (DGBI).¹⁸ The measurement method involves calculating the percentage of time during a 24-hour monitoring period in which the distal esophageal pH value is less

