Research Objectives

The objectives of this study :

Exploring the Effects of Cognitive Behavioral Therapy on Disorders of Esophageal Brain-Gut Axis Dysregulation.

Hypothesis:

- (1) Patients with disorders of esophageal brain-gut axis dysregulation often experience esophageal symptoms due to visceral hypersensitivity and esophageal hypervigilance, which can negatively affect their physical and mental health, sleep, and quality of life. Cognitive Behavioral Therapy (CBT) can help alleviate these symptoms and reduce their impact.
- (2) CBT has been shown to improve symptoms across different subtypes of disorders involving esophageal brain-gut axis dysregulation.

8. Research Methods, Procedures, and Execution Progress

1. Please describe in detail the research methods adopted in this project and the reasons for choosing them.
2. Potential challenges and solutions expected during the project.
3. If this is a continuous project, please also attach the progress report from the previous year or primary data.

Research Method

Participant

This project is a multi -center study. we will recruit cases from three medical centers in Taiwan, We plan to enroll a total of 120 participants, including 40 from our hospital, 40 from Kaohsiung Medical University Hospital, and 40 from E-Da Hospital.

This study is expected to last for 2 years, with the study period ending on December 31, 2025. We intend to recruit participants with esophageal symptoms related to disorders of the gut-brain axis communication from the Gastroenterology outpatient clinics.

Inclusion criteria for participants :

1. Age between 18 and 75 years, with clear consciousness and willingness to sign the informed consent form.

[figure not shown]
Version Date : (Version 8, 11/19/2024)

2. Participants with chronic esophageal symptoms related to esophageal-brain-gut axis communication disorders (such as heartburn, acid reflux, sensation of a foreign body in the throat, difficulty swallowing, chest pain, and chest tightness).

Exclusion criteria for participants :

1. Esophageal stricture, or a history of esophageal, gastrointestinal, or throat surgery.
2. Structural esophageal diseases (e.g., diverticula, esophageal rings), infectious esophagitis, erosive esophagitis, eosinophilic esophagitis.
3. Non-erosive gastroesophageal reflux disease or significant esophageal motility disorders.
4. A history or current diagnosis of esophageal, gastrointestinal, or other organ malignancies.

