5. Significant endocrine or rheumatic autoimmune diseases that may affect gastrointestinal motility.
6. Continuous use of medications that may affect esophageal motility (e.g., anticholinergics, morphine-like drugs, nitrates, calcium channel blockers) within the past month.
7. Use of antidepressants, selective serotonin reuptake inhibitors, or other psychiatric medications within the past three months.
8. Pregnant or breastfeeding women.
9. Individuals with mental disorders or those unable to cooperate.
10. Known allergy to tricyclic antidepressants.
11. Known allergy to selective serotonin reuptake inhibitors.
12. Known allergy to any component of proton pump inhibitors.

Research Design Flowchart

Steps to Follow

In this study, All participants will undergo questionnaire assessments and heart rate variability measurements before treatment. The questionnaires include the Gastroesophageal Reflux Disease Questionnaire (GERDQ), PROMIS GERD, DSI & GSS, RSI, Brief Esophageal Dysphagia Questionnaire (BEDQ), Esophageal Hypervigilance and Anxiety Scale (EHAS), Visceral Sensitivity Index (VSI), Sleep and Mental Health Questionnaires (Sleep Habits Questionnaire PSQI, Taiwanese Depression Questionnaire TDQ, State-Trait Anxiety Inventory STAI, Functional Dyspepsia (FD) Questionnaire, Irritable Bowel Syndrome (IBS) Questionnaire, Quality of Life Questionnaire SF-12, and Northwest Esophageal Quality of Life Scale (NEQOL). Heart rate variability will be measured using the non-invasive "Mind Technology" biofeedback system (Taiwan FDA Medical Device Certification No. 011374).

Following this, a single-blind trial will be conducted with computer-generated random allocation. Participants will receive either 6 weeks of Cognitive Behavioral Therapy (CBT) or 6 weeks of lifestyle management (sham control), with one 1-hour session per week. After 6 weeks of counseling, participants will undergo a final questionnaire assessment and heart rate variability measurement after the 12th week of enrollment. The questionnaires and measurements will take approximately 20 to 30 minutes to complete, marking the end of the trial.

Cognitive Behavioral Therapy (CBT) will be carried out according to the following steps :

(1) Education and Initial Follow-up

Version Date : (Version 8, 11/19/2024)

- (2) Heart Rate Variability and Breathing Introduction
- (3) Cognitive Restructuring and Breathing Application
- (4) Cognitive Diffusion and Behavioral Experiments

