- (5) Problem-Solving and Emotion-Focused Coping Strategies
- (6) End of Treatment and Relapse Prevention

Lifestyle Management (Sham Control) will be carried out according to the following steps :

- (1) Education and Initial Follow-up
- (2) Dietary Habits: What, When, Where, Why
- (3) Changing My Diet: Strategies and Barriers
- (4) Lifestyle Factors: Alcohol, Smoking, and Sugar
- (5) Lifestyle Factors: Sleep and Exercise
- (6) End of Treatment and Relapse Prevention

In this study, we will use non-invasive physiological signal sensors connected to a biofeedback system to measure the participants' physiological signals, including electrocardiogram (ECG) and breathing. Before measurement, participants will first apply ECG electrodes for a two-lead ECG measurement, which will then be converted into heart rate variability (HRV) indicators. Simultaneously, a non-invasive breathing sensor will be used to measure the respiratory rate per minute. Except for a very small number of participants who may experience allergic reactions to the ECG electrodes, the likelihood of side effects is less than 1%.

Multicenter Communication and Coordination Method

The hospital directors of the participating institutions and the principal investigator, [name], will communicate and coordinate via email and a Line group established for the project. The research data collected by each center will be managed and stored by the respective center's director. The hospital directors will assist in consolidating the research data from their institution, and the electronic data will be coded for identification. After the data is compiled, it will be sent back to the principal investigator. Additionally, the research physicians and staff at each participating center will have regular video conferences (every 2 months) to discuss and report on the progress of the study.

Statistical Analysis

All data will undergo normality testing using the Kolmogorov-Smirnov test. If continuous variables follow a normal distribution, they will be expressed as means and standard deviations; if not, they will be presented as medians and interquartile ranges.

For categorical variables, the Chi-square test or Fisher's exact test will be used for analysis. Continuous variables that are normally distributed will be analyzed using the unpaired t-test, while non-normally distributed continuous variables will be analyzed using the Mann-Whitney U test.

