For comparisons involving more than three groups, if the data are normally distributed, an ANOVA with post hoc tests will be conducted. If the data are non-normally distributed, the Kruskal-Wallis test will be applied. A p-value of less than 0.05 will be considered statistically significant.

Statistical analyses will be performed using SPSS 19 for Windows (SPSS, Inc., Chicago, IL, USA).

Clinical Significance and Originality of This Study

1. The originality of this study lies in its use of visceral sensitivity, mind-body connection, esophageal hypersensitivity, anxiety questionnaires, and functional gastrointestinal questionnaires to explore the effects of neuromodulators on diseases related to esophageal-brain-gut axis communication abnormalities. Patients with such conditions often experience more severe esophageal symptoms due to excessive visceral sensitivity and esophageal hypersensitivity.
2. This study aims to establish a model for Cognitive Behavioral Therapy (CBT) in disorders of esophageal brain-gut axis dysregulation. Our research examines the role of CBT in esophageal brain-gut axis dysregulation and refractory gastroesophageal reflux disease (GERD). The results obtained from this study will deepen our understanding of the pathophysiological mechanisms of esophageal brain-gut axis dysregulation and refractory GERD. The findings will help elucidate the etiology of refractory GERD, particularly when patients with GERD also present with esophageal brain-gut axis dysregulation, which leads to a lowered threshold for esophageal symptom perception. This condition can be reversed and improved through the aforementioned treatments. Furthermore, it will assist in early clinical intervention for patients with brain-gut axis communication disorders, enabling the establishment of personalized treatment strategies and the achievement of precision medicine for such patients.

9.Expected Work Items and Specific Outcomes

- (1) Please list the expected tasks to be completed within the execution period.
- (2) Expected contributions to academic research and other applied areas.
- (3) Expected training that participants will receive.

(1) Work items expected to be completed.

In this study, we will also explore the effects of Cognitive Behavioral Therapy (CBT) on disorders of esophageal brain-gut axis dysregulation, as well as its impact on physical and mental health and quality of life.

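### Symptom-specific scales such as the BEDQ are tested without baseline adjustment across subtypes that by definition lack the symptom, so the effect on that symptom is diluted, heavily if week-12 scores are compared

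*Protocol*

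**What the plan says.** Under Inclusion criteria, the Protocol admits patients with any of several esophageal symptoms, "such as heartburn, acid reflux, sensation of a foreign body in the throat, difficulty swallowing, chest pain, and chest tightness". Under Steps to Follow, all participants complete one battery before treatment and again after week 12. It includes the "Brief Esophageal Dysphagia Questionnaire (BEDQ"), the GERDQ and PROMIS GERD. No scale is named as primary.

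The Rome IV definitions in the Background say of functional chest pain "No associated heartburn or dysphagia", and of globus "Symptoms occur between meals, with no dysphagia or odynophagia". The same section calls functional dysphagia the least common of the five disorders and globus a common one. It gives no expected subtype mix for this trial.

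The Statistical Analysis section tests normality first. Normal variables go to an unpaired t-test, while "non-normally distributed continuous variables will be analyzed using the Mann-Whitney U test"; non-normal variables are summarised by medians and interquartile ranges. The section mentions no baseline adjustment and no symptom subset, and does not say whether the week-12 score or the change is tested.

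**The concern.** Hypothesis 1 is that CBT relieves these patients' esophageal symptoms, and hypothesis 2 extends this to the different subtypes. On a scale that measures one symptom, a patient without that symptom has nothing to lose. Pooling such patients with symptomatic ones does two things to a comparison of week-12 scores.

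- It shrinks the mean difference in proportion to the symptomatic share.
- It adds spread between patients at the floor and patients well above it. That spread has nothing to do with treatment.

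The pile of zeros also makes the scale non-normal, so the stated rule selects Mann-Whitney, which in most of the settings below has less power than the t-test. If more than half of each arm scores zero, the reported medians are zero in both arms whatever CBT does. A null BEDQ result could then be read as CBT failing on dysphagia, when the test had little chance of showing an effect.

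**Working it through.** **Inputs from the Protocol.** "We plan to enroll a total of 120 participants"; "a single-blind trial will be conducted with computer-generated random allocation"; "A p-value of less than 0.05 will be considered statistically significant". The Protocol gives no effect size, SD or power, so there is no calculation of its own to reproduce.

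**Assumptions, none from the Protocol.**
- 1:1 allocation, so 60 per arm, and two-sided testing.
- A share f of patients has the symptom. Their mean is m = 2 SD above the floor, their SD is 1, and the CBT effect in them is d = 0.5 or 0.8 SD.
- All other patients score 0 at both assessments.
- The baseline-final correlation in symptomatic patients is 0.5.

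On the choice of f: two of the five definitions exclude dysphagia, so f would be 3/5 = 60% if the subtypes were equally common and every other patient had dysphagia. A value of 30% represents a mix with more patients at the floor.

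**Reference with nobody at the floor.** 60 per arm gives 78% power for 0.5 SD. The effect detectable with 80% power is 0.51 SD.

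**Week-12 score, all patients.** Mean difference ≈ f × d. Variance ≈ f × 1 + f(1 − f) × m².
- f = 0.6, d = 0.5: difference 0.6 × 0.5 = 0.30; variance 0.6 + 0.24 × 4 = 1.56; SD 1.25.
- Standardised effect 0.30 / 1.25 = 0.24. Simulation gives 0.23, slightly lower because scores are cut off at zero.
- t-test power ≈ Φ(0.24 × √30 − 1.96) = Φ(−0.65) = 0.26. Simulation gives 0.27.

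**Change score, all patients.** Patients at the floor contribute changes of zero, so the between-subtype spread drops out. The variance of change in symptomatic patients is 2(1 − 0.5) = 1, and in the pooled set about f.
- f = 0.6, d = 0.5: standardised effect ≈ 0.30 / √0.6 = 0.39.
- Power ≈ Φ(0.39 × √30 − 1.96) = Φ(0.18) = 0.57. Simulation gives 0.52, against 0.52-0.55 for unadjusted t-tests in symptomatic patients only.

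**Simulated power.** The lower figure is for 0.5 SD, the higher for 0.8 SD.

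| Analysis | 30% symptomatic | 60% symptomatic |
|---|---|---|
| Week-12 score, all, Mann-Whitney | 0.06-0.09 | 0.20-0.42 |
| Week-12 score adjusted for baseline (ANCOVA), all | 0.34-0.69 | 0.61-0.95 |
| ANCOVA, patients symptomatic at baseline | 0.37-0.72 | 0.66-0.96 |

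Repeat runs move these figures by a few hundredths; at 60% and 0.5 SD, Mann-Whitney power ranged from 0.17 to 0.21. At shares of 60% or below, the Kolmogorov-Smirnov test rejected normality in essentially every simulated trial, so Mann-Whitney is the test that the stated rule selects.

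With change scores at 30% symptomatic and 0.8 SD, all-patient power is about 0.57-0.59 (t-test) or 0.47-0.48 (Mann-Whitney).

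**The case against.** The strongest counter-argument is that most of the loss comes from ignoring the baseline score, not from pooling. The baseline is collected, the Protocol does not exclude change scores, and a separate analysis plan may settle this. With change scores or ANCOVA in all patients, power is close to that of the restricted comparison. The remaining shortfall reflects how few patients have the symptom, and restriction cannot cure that. This stands, and it is why baseline adjustment comes first in the fix. It does not remove the point: the stated tests are unadjusted, and even a change score yields an average effect of only about f times the effect in symptomatic patients.

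Three stronger readings are tempting, and the Protocol does not support them.

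- **That a real effect would mostly be hidden.** This holds only for raw week-12 scores and depends on a subtype mix that the Protocol does not give.
- **That the reflux scales suffer equally.** Only functional chest pain excludes heartburn, so far fewer patients need be at the floor on GERDQ or PROMIS GERD. The definitions of functional heartburn and reflux hypersensitivity do not exclude dysphagia either, and the inclusion criterion does not bar coexisting symptoms.
- **That no scale captures each patient's own symptom.** DSI & GSS and RSI are not spelled out, so this is not established. EHAS, VSI and NEQOL are not tied by name to a single symptom.

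Floor scores are themselves inferred from the definitions, since the Protocol does not describe BEDQ scoring.

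**Conclusion.** The point holds as a conditional one. Followed as written, the analysis dilutes the effect on any symptom-specific scale, most clearly the BEDQ, because two of the five subtypes lack dysphagia by definition. If week-12 scores are tested, the dilution is heavy. At 60% symptomatic and 0.5 SD, power falls from 0.78 with nobody at the floor to about 0.2 with Mann-Whitney; at 30% symptomatic it is below 0.10 even for 0.8 SD. If change or baseline-adjusted scores are tested, pooling costs little power, but the reported all-patient average still understates the effect in patients who have the symptom. The sizes rest on the assumed mix, effect, distance from the floor and correlation, and should be quoted as ranges. This is worth correcting because the remedy is cheap. It does not undermine the trial as a whole, since the BEDQ is one of many scales and is not named as primary.

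**What to change.** In the Statistical Analysis section:

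1. Analyse each symptom-specific scale as the week-12 score adjusted for its own baseline score, in all randomised patients.
2. Add a prespecified comparison, also baseline-adjusted, restricted to patients whose baseline score is above the floor, and read the effect on that symptom from it. The baseline precedes random allocation, so the subset keeps the randomised comparison.
3. State that an all-patient null result on such a scale is not evidence of no effect on the symptom.

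Under Steps to Follow, spell out DSI & GSS. If they do not already rate the patient's own qualifying symptom, add one 0-10 rating of it, with the symptom fixed at baseline, at the two existing assessments. A later analysis plan cannot recover a rating that was never collected.

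Cost: a few sentences of analysis text and at most one extra question at two existing assessments. The restricted comparison uses fewer patients and applies only to those with the symptom.

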Previous research has shown that neuromodulators can effectively reduce symptoms in patients with irritable bowel syndrome (IBS) or functional dyspepsia by modulating visceral hypersensitivity through central and peripheral mechanisms.^{35,36} Therefore, using neuromodulators to regulate visceral hypersensitivity and esophageal hypervigilance in esophageal brain-gut axis communication disorders is considered a feasible strategy. However, a systematic review of the literature shows that among the few available randomized controlled trials, the efficacy of neuromodulators in the various subtypes of esophageal brain-gut axis communication disorders is inconsistent.³⁷ Therefore, whether neuromodulators can be widely used in the treatment of these disorders still requires more supporting evidence.

Cognitive Behavioral Therapy (CBT) is a form of psychological treatment that functions as a brain-gut axis intervention. It can modify the pain perception pathways of the brain-gut axis, reduce hypervigilance and symptom-specific anxiety, and is considered effective in improving chronic esophageal symptoms associated with disorders of brain-gut axis communication.

This approach includes the measurement of Heart Rate Variability (HRV), which involves collecting raw electrocardiogram signals through a biofeedback system or using photoplethysmography (PPG) sensors to detect pulse wave signals. These signals are then converted into HRV indicators, which serve as markers of autonomic nervous system activity.

Heart Rate Variability Biofeedback (HRVB) can enhance HRV indices and has been shown to be effective in individuals with physical illnesses, psychological disorders, and even in healthy populations.^{38, 39}

Recent studies have shown that Cognitive Behavioral Therapy (CBT) can improve esophageal symptoms and quality of life in individuals with supragastric belching and non-erosive reflux disease (NERD).⁴⁰⁻⁴² Currently, Cognitive Behavioral Therapy (CBT) for gastrointestinal disorders typically involves 6 to 8 therapy sessions. In this study, participants will undergo either six weeks of CBT or lifestyle management, administered by psychologists trained in CBT and conducted in accordance with the clinical guidelines of the American Gastroenterological Association (AGA).⁴³

[figure not shown]

Figure 2. The primary goal of Cognitive Behavioral Therapy (CBT) is to modify maladaptive thoughts and behaviors in order to reduce esophageal hypervigilance.

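### Does calling the lifestyle-management arm a sham control misstate what the trial compares?

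*Protocol*

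**What the plan says.** The comparison is described under Steps to Follow in Section 8. Participants are randomised to six weeks of CBT or to "6 weeks of lifestyle management (sham control), with one 1-hour session per week". The list of control sessions that follows carries the same label: "Lifestyle Management (Sham Control) will be carried out according to the following steps".

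The control's session titles include "Changing My Diet: Strategies and Barriers", "Lifestyle Factors: Alcohol, Smoking, and Sugar" and "Lifestyle Factors: Sleep and Exercise". One further session deals with eating habits. The first session has the same title as the first CBT session, and both programmes close with "End of Treatment and Relapse Prevention".

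The background in Section 7 says that "participants will undergo either six weeks of CBT or lifestyle management, administered by psychologists trained in CBT". Steps to Follow uses one word for what both arms receive: "After 6 weeks of counseling, participants will undergo a final questionnaire assessment and heart rate variability measurement after the 12th week of enrollment".

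The Project Abstract gives the primary objective as the efficacy of CBT in esophageal disorders of gut-brain interaction. Research Objectives in Section 7 speaks of the effects of CBT. Neither names a comparator, and neither do the two hypotheses. Hypothesis 1 lists sleep among the things these disorders impair, and a sleep questionnaire (PSQI) is among the measures.

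**The concern.** Sham suggests a procedure with no therapeutic content. The titles here describe advice that patients could act on, given by CBT-trained psychologists for as many hours as CBT. If that advice helps, the difference between arms is smaller than the full effect of CBT.

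With an inert-sounding label and no comparator in the objective, a null difference could be reported as CBT being ineffective. It would show only that no difference from lifestyle counselling was found. Sleep looks most exposed: it is measured, it appears in Hypothesis 1, and only the control has a session with sleep in its title.

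A side issue concerns heart rate variability. It is named in one CBT title and breathing in two, while neither appears in a control title. A difference in that measure might therefore partly reflect a practised skill.

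**Working it through.** **1. The two programmes side by side** (topics paraphrased from the lists in Section 8)

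| Session | CBT | Lifestyle management |
|---|---|---|
| 1 | Education, first follow-up | Same title |
| 2 | Heart rate variability and breathing | Eating habits |
| 3 | Restructuring of thoughts, use of breathing | Changing the diet |
| 4 | Cognitive diffusion, behavioural experiments | Alcohol, smoking, sugar |
| 5 | Problem-solving, coping | Sleep, exercise |
| 6 | Closing, preventing relapse | Same title |

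- Sessions: 6 against 6, each one hour and weekly.
- Identical titles: 2 of 6.
- Lifestyle topics by title: 4 of 6 in the control, 0 of 6 in CBT.
- Sleep by title: 1 of 6 in the control, 0 of 6 in CBT.
- Providers: the Section 7 sentence covers both arms.

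The randomised contrast is therefore CBT minus lifestyle management. The description of the label as loose is correct.

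**2. Is the comparator hidden or contradicted?** No. The Section 7 background, Steps to Follow and the heading of the control list all name lifestyle management. In the last two, sham is only a parenthesis after that name. No sentence says that the control is inert or expected to do nothing. None says that a null difference means CBT has failed.

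**3. Does the label affect any number?** The protocol gives no effect size, standard deviation or power for its total of 120, so there is no stated calculation to reproduce. For illustration I assume 1:1 allocation (60 per arm), no loss, and a two-sided t-test at 0.05. All effects are assumed.

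- True contrast = CBT effect over an inert control − control effect over an inert control.
- Noncentrality = contrast × √(60/2) = contrast × 5.477; critical t on 118 degrees of freedom ≈ 1.980.
- Example: 0.50 × 5.477 = 2.739; 2.739 − 1.980 = 0.759; power ≈ 78%.

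| CBT effect (SD) | Control effect (SD) | Contrast (SD) | Power |
|---|---|---|---|
| 0.50 | 0 | 0.50 | 78% |
| 0.50 | 0.1 | 0.40 | 58% |
| 0.50 | 0.2 | 0.30 | 37% |
| 0.50 | 0.3 | 0.20 | 19% |

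Power falls quickly if lifestyle counselling works. The inputs, however, are the two treatment effects and the sample size, and the control's name is not one of them. Each row is the same whether the arm is called sham, attention-matched or lifestyle management. The table describes the choice of control, which is defensible, and says nothing about the label. The documents give no effect for the control, so they do not show which row applies.

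**4. Sleep.** The argument rests on titles alone. A CBT title without the word sleep does not show that CBT leaves sleep out, and Hypothesis 1 expects CBT to lessen the impact of these disorders, sleep included. PSQI is one of many questionnaires and is not designated primary.

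**5. Heart rate variability.** The final recording comes after week 12, some weeks after a six-week programme. Respiratory rate is recorded at the same time, so an effect of breathing can be examined. The protocol does not claim that this measure proves clinical benefit. Posture, display and breathing instructions are details of the recording procedure.

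**The case for a change.** The best case for a change is that the objective and the name of the control are fixed in the protocol itself, so this is not something left to an analysis plan. The closing sections speak confidently of the condition being improved by treatment and of establishing the role of CBT. The planned between-arm tests can support only a relative claim. A few words would prevent a misreading: a more accurate name for the control, an objective worded as CBT compared with lifestyle management, and a sentence on what a null result means.

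Part of this stands. Sham is not the best word for a counselling programme with real content, and an objective that names its comparator is better than one that does not. An author who revises the text for other reasons could reasonably make both edits.

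The rest does not carry a required change. Harm needs three things together: a null result, a control that truly works, and an author or reader who passes over a comparator set out session by session. The risk also runs one way. If the control has some benefit, a positive result is conservative for CBT. The sentence on null results is reporting advice and corrects nothing that the protocol states. The expectations in the closing sections are not decision rules.

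**Conclusion.** The observation is accurate and small: a contact-matched lifestyle-counselling programme is labelled a sham, and the objective omits the comparator. No change to the plan is needed. The methods disclose the comparator fully, and the control is a fair choice because it matches CBT in number and length of sessions and in provider while leaving out, by title, the cognitive and coping content under test. Relabelling would alter no session, outcome, test, sample size or power, so its numerical effect is nil.

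This conclusion rests on session titles, since fuller content is not given. It does not depend on whether lifestyle counselling relieves these symptoms, which the protocol does not show. Any difference found is to be read as CBT relative to lifestyle management, which an analyst working from Section 8 would do in any case.
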